6.6. Quality of Life

6.6.1 Objective

To investigate if change in quality of life (QOL) from baseline to 3 months, and 1 year, respectively, after randomization differ in the two treatment groups.

6.6.2 Endpoint

Change in quality of life (QOL) from baseline to 3 months, and 1 year, respectively, after randomization (Quality of life will be assessed by the EuroQoL-5D).

6.6.3 Statistical Hypothesis, Model and Method of Analysis

The statistical null hypothesis is that there is no change in quality of life (QOL) from baseline to 3 months, and 1 year, respectively, after randomization (Quality of life will be assessed by the EuroQoL-5D).

Within and between treatment group comparisons will be made with Wilcoxon signed rank test and Mann-Whitney U test, respectively.

7. Sensitivity Analysis

A sensitivity analysis on all endpoints will be performed on patients enrolled according to protocol version 4.0 and 5.0 to investigate any potential differences in study results related to the change in study design due to the update of the European guidelines. The analyses will be performed using both PPS and SAS.

Heterogeneity in the treatment effect between sites and PTP groups will be investigated. An interaction analysis between the randomization variable and site will be made.

8. Missing Data

Data will be analysed for potential extreme outliers. If present, each outlier will be investigated.

However, outliers will be included in the analysis, except if a clinical cause can be excluded.

9. References

Task Force Members, Montalescot G, Sechtem U, Achenbach S, Andreotti F, Arden C, et al. 2013 ESC guidelines on the management of stable coronary artery disease: the Task Force on the management of stable coronary artery disease of the European Society of Cardiology. *Eur Heart J*. 2013 Oct;34(38):2949–3003

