4.2. Statistical Hypothesis, Model and Method of Analysis

Statistical Hypothesis

The statistical null hypothesis is that there is no difference between a PTP plus CAD-score guided rule-out strategy and a PTP guided strategy alone at one year in reducing diagnostic procedures (π) in patients with symptoms suggestive of stable CAD.

$$H_0: X/\pi_{PTP+CAD-score} = X/\pi_{PTP}$$

The alternate hypothesis is that a PTP plus CAD-score guided rule-out strategy is superior to a PTP guided strategy alone at one year in reducing diagnostic procedures (π) in patients with symptoms suggestive of stable CAD.

$$H_A: X/\pi_{PTP+CAD-score} \neq X/\pi_{PTP}$$

Statistical Model and Method of Analysis

The cumulative numbers of diagnostic test will be assessed using Poisson based test and visually by Nelson-Aalen nonparametric estimator.

Total numbers of patients undergoing diagnostic procedures will be presented as total numbers divided into categories of numbers of procedures: Categories: [0, 1, 2, 3+ diagnostic procedures].

The analyses are performed on **FAS** in accordance with the intention-to-treat principles.

A reduction of 15 % or more in the primary endpoint is regarded as clinically significant.

Sample size

A sample size of 521 provides 80 % power with an alpha significance level of 0.05 for testing superiority in terms of numbers of NIT between the control and intervention group.

The power calculation is based on the study design applicable when the study was initiated (Protocol version 3.0) which reflected the European guidelines from 2013 (Montalescot G *et al.* 2013). Protocol version 4.0 and 5.0 reflects the updated European guidelines from 2019 (Knuuti *et al.* 2019), however, the power calculation remains unchanged and a note provides an explanation for each section below.

The main analysis will be based on intention to treat. The study allows for some degree of cross-overs where patients ruled out instead are crossed-over to a NIT. The power calculation simulates a worst-case scenario where the two groups have the lowest expected difference in number of diagnostic procedures; 0% of patients with DF <15% crossed-over to NIT in the control group and 20% of patients with a CAD-score ruling out obstructive CAD in the intervention crossed-over to NIT.

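### SAP section 7 sets out to study differences due to the design change, but specifies no version 3.0 estimate and no contrast between protocol versions

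*SAP*

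**What the plan says.** Section 4.2 explains that enrolment began under version 3.0, built on the 2013 European guideline, and that "Protocol version 4.0 and 5.0 reflects the updated European guidelines from 2019". Section 6.2.1 (objective B) adds that PTP means the Diamond-Forrester score for version 3.0 patients and the ESC 2019 probability for later patients.

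Section 7 responds to this change as follows:

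- Population: the sensitivity analysis, which covers every endpoint, "will be performed on patients enrolled according to protocol version 4.0 and 5.0 to investigate any potential differences in study results".
- Aim: "to investigate any potential differences in study results related to the change in study design due to the update of the European guidelines".
- Analysis sets: "The analyses will be performed using both PPS and SAS".
- Other heterogeneity: "Heterogeneity in the treatment effect between sites and PTP groups will be investigated", followed by "An interaction analysis between the randomization variable and site will be made".

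The primary analysis in section 4.2 is on a different set: "The analyses are performed on FAS in accordance with the intention-to-treat principles". The subgroup list in section 4.3, which is to be analysed with Poisson interaction models, does not include protocol version. Section 1 names site and PTP as the stratification factors.

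**The concern.** Asking whether results differ because the design changed needs an effect before the change, an effect after it, and a measure of the difference with its uncertainty. Section 7 supplies only the second. It specifies an interaction for site but none for version, although the version change is the reason given for the sensitivity analysis.

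The change matters to the comparison itself. PTP selects patients for testing in both arms, so a new PTP tool changes both randomised strategies. The pooled primary result averages over the two periods, and readers will want to know whether the effect was similar in both. As planned, they can only set the subset result beside the pooled result, informally and across different analysis sets.

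**Working it through.** **Is the contrast specified anywhere?** No figure in the SAP is in dispute, so the first step is to compare sections.

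- Section 7: version 4.0/5.0 only; interaction with site; heterogeneity by site and PTP group.
- Section 4.3: several PTP splits, age, sex, risk factors and body mass index; no version.
- Sections 4.2, 5.2 and 6.1 to 6.6: no analysis by version.

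The PTP-group analyses do not fill the gap. PTP group is a risk category, not a protocol version, and by section 6.2.1 it is measured with a different tool in each period.

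**What does subset against pooled show?** Let *f* be the share of patients enrolled under version 3.0 (not in the SAP), and E3 and E45 the log rate ratios in the two cohorts. On one common analysis set, approximately:

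- pooled = f·E3 + (1 − f)·E45
- E45 − pooled = f·(E45 − E3)

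As an assumed illustration, take the SAP's planned ratio 0.77/0.94 = 0.82 under version 3.0 and 1.00 under 4.0/5.0. The pooled ratio is then 0.98 (f = 10%), 0.95 (f = 25%) or 0.91 (f = 50%), against 1.00 in the subset. The visible gap is smaller than the true one. Its standard error shrinks by the same factor *f*, so the overlap makes the gap look small without losing evidence.

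**The analysis sets differ.** The formula above needs one common set. Section 4.2 uses the FAS by allocated group. Section 7 uses the PPS and SAS, and section 2 counts patients who missed their allocated CAD-score measurement in the control group for the per-protocol analysis. The subset and pooled results would therefore differ in more than version.

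**What would a version term deliver?** Inputs: 0.94 and 0.77 procedures per patient (section 4.2); about 2000 patients randomised 1:1 (section 1), hence 1000 per arm; two-sided alpha 0.05; Poisson variance. The share *f* is assumed.

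- Variance of a cohort's log rate ratio with n per arm: (1/0.94 + 1/0.77)/n = 2.3625/n
- Interaction SE = √[2.3625/(1000f) + 2.3625/(1000(1 − f))]
- Detectable ratio of rate ratios at 80% power = exp[(1.960 + 0.842)·SE]
- Power for a true log difference D = Φ(D/SE − 1.960)

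With the full planned effect in one version and none in the other, D = ln(0.94/0.77) = 0.1995:

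| f | SE | Detectable ratio, 80% power | Power |
|---|---|---|---|
| 10% | 0.162 | 1.57 | 23% |
| 25% or 75% | 0.112 | 1.37 | 43% |
| 50% | 0.097 | 1.31 | 54% |

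For a milder assumed change, rate ratio 0.82 under version 3.0 and 0.92 under 4.0/5.0 with f = 30%: SE = √[2.3625/300 + 2.3625/700] = 0.106; D = ln(0.92/0.82) = 0.115; D/SE = 1.085; power = Φ(−0.875), about 19%.

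At f = 30% the 95% interval for the ratio of rate ratios runs from the estimate divided by 1.23 to the estimate times 1.23, since exp(1.96 × 0.106) = 1.23.

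**The case against.** The strongest defence is that repeating the analysis in the cohort enrolled under the current design is a recognised sensitivity analysis and answers a useful question: what is the effect under the 2019 guideline? That stands. A reader might infer that the trial cannot say how the strategy performs under that guideline; section 7 estimates exactly that, so the inference is not supported.

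A reader might also infer that the overlap between subset and pooled result hides a real change. The algebra does not support this. On a common analysis set the gap and its standard error shrink together, and E3 could be recovered from the two results and the cohort sizes. What remains is that the SAP specifies neither that calculation nor a common analysis set.

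The sponsor may add that section 4.2 expects only a slight change in the patient pathway. Yet the same note raises the requirement from 314 to 521 per arm. It is tempting to go further. If only the expected difference had changed, it would scale to about 0.17 × √(314/521) = 0.13 procedures per patient, or 14% of 0.94, just under the 15% called clinically significant. The SAP does not give the revised rates or say what drove the increase, so this is not established. It shows only that some change was foreseen.

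Finally, an interaction term would often miss a real change. This stands too, and it limits what the remedy can deliver.

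**Conclusion.** The point holds as a gap between the aim of section 7 and its method. The SAP plans no version 3.0 estimate, no version contrast and no interval for one. The only informal comparison mixes version with analysis set. This conclusion rests on the text alone and needs no assumption.

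The consequence is limited. The gap does not undermine the validity of the primary analysis or its error control, and the documents do not support reading it that way. Nor would a difference between versions prove that the guideline caused it, because version coincides with calendar time.

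The power range of about 20% to 55% depends on an assumed version 3.0 share of 10% to 75%, assumed effects, Poisson variance and 1000 patients per arm.

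**What to change.** In section 7:

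1. Keep the version 4.0/5.0 analysis, but run it on the FAS so that it matches the primary analysis.
2. Report the version 3.0 estimate beside it, each with a 95% confidence interval, for the primary endpoint, MACE and the other endpoints.
3. For the primary endpoint, add protocol version (3.0 vs 4.0/5.0) and its interaction with randomised group to the Poisson model of section 4.3. Report the ratio of rate ratios with its 95% confidence interval.
4. State that the term is descriptive: it is not a pass/fail test, and a difference may reflect calendar time as well as the guideline.

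The cost is a few lines of SAP text and one more interaction model. Enrolment version must already be known, since section 7 selects patients by it. No new data or patients are needed. The drawback is imprecision: the version 3.0 estimate and the interaction may have wide intervals, so a result that shows no clear difference should not be reported as evidence that the effect was the same.

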6.5.1 Objectives	13
6.5.2 Endpoints.....	14
6.5.3 Statistical Hypothesis, Model and Method of Analysis	14
6.6. Quality of Life	14

6.6.1 Objective.....	14
6.6.2 Endpoint	15
6.6.3 Statistical Hypothesis, Model and Method of Analysis	15
7. Sensitivity Analysis.....	15
8. Missing Data	15
9. References	15

1. Background and Study Design

The FILTER-SCAD trial is a randomized, controlled, multicentre, superiority trial with two parallel groups investigating the use of the acoustic measured risk score (CAD-score) for obstructive coronary artery disease (CAD) for ruling out CAD as compared to current standard diagnostic strategy in patients with symptoms suggestive of CAD.

Approximately 2000 patients with symptoms suggestive of CAD referred for outpatient assessment are expected to be enrolled at 5 study sites in Denmark and 1 in Sweden. The subjects will be randomized 1:1 to either 1) standard diagnostic strategy i.e. pre-test probability (PTP) stratification followed by non-invasive test (NIT), if indicated (control group), or (2) PTP plus CAD-score stratification followed by NIT, if indicated (intervention group). Randomization is stratified according to study site and PTP. Given the stratified design, all analyzes are carried out stratified by site and PTP.

2. Analysis Datasets

All patients from whom written informed consent are obtained will be included in the **full analysis set (FAS)**. Subjects will be analysed according to the allocated randomization group in accordance with the intention-to-treat principles.

The **per protocol set (PPS)** will include the subjects from the FAS who did *not* have one of the following major protocol violations:

- inclusion criteria not met
- exclusion criteria met
- no PTP calculation
- no CAD-score measurement (intervention group only).

Patients who did not receive the randomly allocated CAD-score measurement will be included and analysed in the control group (per protocol analysis).

The **screened analysis set (SAS)** will include all screened patients who receive a subject number.

3. Demographics and Baseline Characteristics

Continuous variables will be presented as mean and standard deviation for variables following a normal distribution or as median with interquartile range if showing a skewed distribution. Categorical variables will be presented as frequencies and percentages. Categorical data will be compared using Fisher's exact

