4.1. Primary endpoint

Difference between the two treatment groups in cumulative number of non-invasive and invasive diagnostic procedures, assessed at 1 year after randomization. NITs include exercise ECG, CCTA, Rb-PET CT, MPI, CMRI and stress echocardiography. Invasive procedures include invasive coronary angiographies (ICA) only.

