5.2. Statistical Hypothesis, Model and Method of Analysis

Statistical Hypothesis

The statistical null hypothesis is a PTP plus CAD-score guided rule-out strategy is inferior in terms of safety outcomes MACE (π) in patients with symptoms suggestive of stable CAD at one year when using a pre-specified non-inferiority margin (δ) as compared to a standard PTP guided strategy.

$$H_0 = \pi_{PTP+CAD-score} - \pi_{PTP} \geq \delta$$

The alternate hypothesis is that a PTP plus CAD-score guided rule-out strategy is non-inferior to a standard PTP-guided strategy in terms of MACE in patients with symptoms suggestive of stable CAD at one year when using a pre-specified non-inferiority margin (δ).

$$H_A = \pi_{PTP+CAD-score} - \pi_{PTP} < \delta$$

Statistical Model and Method of Analysis

The absolute risk difference between treatment groups will be compared to a non-inferiority margin (δ) of 1.5% using a two-sided 95% confidence interval applying a continuity-corrected modification of the Wilson's score method. Based on previous studies (Therming *et al* 2018) the obstructive CAD prevalence is expected to be 6.5% and the event rate in each group is expected to be 1.3% at 1-year FU.

Moreover, data will be analyzed using stratified proportional hazard Cox regression and visually by Kaplan Meier curves.

Sample size

A sample size of 1914 provides 90% power with an alpha significance level of 0.05 for testing non-inferiority in terms of MACE between the control and intervention group.

This sample size calculation is based on the hypothesis of non-inferiority in terms of MACE in the group of patients with DF-score and CAD-score stratification prior to NIT compared with the group of patients with standard care strategy of DF-score stratification prior to NIT. It is assumed that in the control group, 50% of the patients with a DF-score <15% are ruled out of obstructive CAD without further testing, and 50% are referred for further testing. Based on previous studies (Therming *et al* 2018) the obstructive CAD prevalence is expected to be 6.5% and the event rate in each group is expected to be 1.3% at 1-year FU. The non-inferiority margin is set to 1.5%.

The assumed annual MACE event rates for different patient categories are:

- Clean arteries (CACS=0 and no stenosis): 0.4%

- Non-obstructive CAD: 1.2%
- Diagnosed CAD: 6.9%
- Unobserved CAD: 10.0%

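### SAP Section 8 (Missing Data) holds only an outlier rule that could remove true values after inspection, and the MACE margin test has no rule for patients without 1-year status

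*SAP*

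**What the plan says.** Section 8 is titled Missing Data. Its whole content is a check for outliers, "Data will be analysed for potential extreme outliers. If present, each outlier will be investigated", followed by the exclusion rule, "However, outliers will be included in the analysis, except if a clinical cause can be excluded". It does not say what counts as extreme, which variables are meant, who decides, when, or whether that person is blind to arm. It says nothing about missing values.

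The primary endpoint in Section 4.1 is a count: "Difference between the two treatment groups in cumulative number of non-invasive and invasive diagnostic procedures, assessed at 1 year after randomization". Section 4.2 gives the method: "The cumulative numbers of diagnostic test will be assessed using Poisson based test and visually by Nelson-Aalen nonparametric estimator". It also gives the population: "The analyses are performed on FAS in accordance with the intention-to-treat principles". Section 2 defines that population by consent alone, so membership does not depend on 1-year data being available.

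For the key secondary endpoint, Section 5.2 states: "The absolute risk difference between treatment groups will be compared to a non-inferiority margin". The margin is 1.5 percentage points and the interval is a two-sided 95% continuity-corrected Wilson-type interval. Stratified Cox regression and Kaplan-Meier curves are listed as additional analyses. Section 7 varies protocol version, analysis set, site and PTP, but not assumptions about missing data.

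**The concern.** There are two separate problems.

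**The outlier rule.** The primary endpoint is a right-skewed count, and its extreme values are patients who had many tests. The trial asks whether a strategy reduces testing, so a patient tested repeatedly without clear clinical need is part of the effect being measured. A rule that can remove a value once a clinical cause is ruled out could remove just such patients. If someone who knows the arm makes that judgement after seeing the data, the exclusions may differ between arms and the randomised comparison is no longer protected.

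**The MACE proportion.** A simple proportion at 1 year needs a numerator and a denominator for every patient. The SAP does not say whether a patient without 1-year status is kept, dropped or counted up to the last contact. With an expected 13 events per 1000, a handful of unseen events can decide the non-inferiority result.

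**Working it through.** **Inputs from the SAP.** Expected means are 0.94 (control) and 0.77 (intervention) procedures per patient, and a 15% reduction is regarded as clinically significant (Section 4.2). The MACE rate is 1.3% per arm with a margin of 1.5 points (Section 5.2). About 2000 patients are randomised 1:1 (Section 1), so 1000 per arm is used. **Assumptions, because the SAP gives none:** the outlier cut-off, the number excluded, the shape of the count distribution, the share lost and the risk among those lost.

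**1. Primary endpoint, planned contrast.** Difference 0.94 − 0.77 = 0.170. Ratio 0.77/0.94 = 0.819, a reduction of 18.1%.

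**2. Same cut-off in both arms.** For a Poisson count with mean m, after dropping counts of c or more, the mean is m × P(X ≤ c−2) / P(X ≤ c−1). With c = 5:
- control 0.928 (0.28% of patients removed)
- intervention 0.765 (0.12% removed)
- difference 0.163, ratio 0.824, reduction 17.6%.

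**3. Exclusions that differ by arm.** Remove ten patients with 5 procedures each from 1000.
- Control only: (940 − 50)/990 = 0.899; ratio 0.77/0.899 = 0.857, reduction 14.3%.
- Intervention only: (770 − 50)/990 = 0.727; ratio 0.727/0.94 = 0.774, reduction 22.6%.
- Both arms: 0.727/0.899 = 0.809, reduction 19.1%.

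Ten such patients per 1000 is more than a Poisson count would give in control (about 2.8 per 1000 with 5 or more), so this case supposes a heavier tail. With only the Poisson share removed from control, the ratio is 0.77/0.928 = 0.830, a reduction of 17.0%.

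**4. MACE.** The upper limit for the difference is d + √[(u₁ − p₁)² + (p₂ − l₂)²], where l and u are the continuity-corrected Wilson limits of each arm (1 = intervention, 2 = control). For 13/1000, l = 0.00724 and u = 0.02274. For 17/1000, l = 0.01026 and u = 0.02767.

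| Events, intervention v control (of 1000 each) | Upper limit, points | Against 1.5 |
|---|---|---|
| 13 v 13 | 1.13 | pass |
| 16 v 13 | 1.49 | pass |
| 17 v 13 | 1.61 | fail |
| 17 v 17 | 1.26 | pass |

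For 17 v 13: 0.004 + √(0.010665² + 0.005756²) = 0.0161.

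**5. How much loss this takes.** If a share s of the intervention arm is lost and carries k times the 1.3% risk, while control is unaffected, the true events per 1000 are 13(1 − s) + 13ks.
- s = 5%, k = 5: 15.6 events, upper limit 1.44, pass.
- s = 10%, k = 3: 15.6 events, 1.44, pass.
- s = 10%, k = 5: 18.2 events, 1.75, fail.

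**6. Incomplete counts in the primary analysis.** If lost patients were entered as zero procedures, equal 5% loss leaves the ratio at 0.819. Loss of 10% in intervention and 5% in control gives (0.77 × 0.90)/(0.94 × 0.95) = 0.776.

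**The case against.** The rule makes inclusion the default, calls for each outlier to be investigated, and lets a value go only if a clinical cause is positively excluded. The sponsor may well have meant artefacts and recording errors only. A performed test is itself a clinical event, so its cause would be hard to exclude. This is a fair reading, but the text does not limit the rule to errors and says nothing about blinding.

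Several stronger readings are tempting and are not supported:
- **That everyone with 3 or 4 procedures would be dropped.** Section 4.2 reports three or more procedures as an ordinary category, so such patients are hardly extreme. Even dropping counts of 4 or more in both arms leaves a 16.4% reduction under Poisson counts (0.743/0.888 = 0.836).
- **That the rule distorts the dose or MACE endpoints.** Section 6.5.3 compares contrast and radiation dose by a rank test, which a few extremes hardly move. A binary outcome has no outliers to remove.
- **That the gap between 2000 planned and 1914 required is an expected loss of 43 per arm.** The SAP does not call it a dropout allowance.
- **That lost patients will be counted as event-free.** The SAP nowhere says so. It leaves the matter open.
- **That intention to treat is already broken.** The rule permits a departure; it does not show that one will occur.

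The planned Cox, Kaplan-Meier and Nelson-Aalen methods do allow for censoring. They sit beside the Poisson test and the margin test, however, and do not govern them. A protocol not seen here may add rules, but the SAP has its own section under this title, and it also defines the margin test that needs the denominator.

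**Conclusion.** The point stands as a defect of wording and method that should be corrected before the data are examined. The outlier rule leaves open the removal of true procedure counts after inspection. Its effect is small when both arms are treated alike, and in the one-arm case it becomes material only with a heavy tail or a low cut-off. For MACE, the conclusion is sensitive to as few as four unseen events if they all fall in the intervention arm, but robust if they fall equally. That reversal needs either substantial loss or a risk among the lost several times the expected 1.3%. All of these sizes rest on assumed cut-offs, exclusions and losses, because the SAP supplies none.

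**What to change.** 1. Replace the outlier rule in Section 8 with: *All recorded values of randomised patients are kept; a value is corrected or set to missing only if source data show a recording error, decided blind to arm before database lock.*
2. For MACE, base the 1-year risk difference on the Kaplan-Meier estimates already planned, so that patients who leave early contribute their observed time. Alternatively, keep the Wilson-type interval as the main test, state its denominator rule, and add the Kaplan-Meier difference as a sensitivity analysis.
3. Because Kaplan-Meier assumes that loss is unrelated to risk, add a tipping-point table giving the number of unseen events, by arm, that would reverse non-inferiority.
4. In the primary Poisson analysis, use follow-up time as an offset for patients with incomplete follow-up.

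The cost is a few lines of SAP text, one extra table and slightly more analysis work. No new data are needed.
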